9.2.2 Acne Lesion Count

The investigator/designee will perform a count of inflammatory lesions (papules, pustules and nodules) and non-inflammatory lesions (open and closed comedones) and will be conducted after the IGA assessment is completed. Lesion counts are confined to the face (including forehead, nose, cheeks, and chin) and exclude submental lesions. Where possible, the same efficacy assessor should perform all lesion count assessments on the same subject at all visits. Individuals performing the acne lesion counts will be trained and certified prior to conducting any assessments on the study. Lesion counts will be entered into the eCRF.

9.3 Other Assessments

9.3.1 Photographs

Photographs of the face will be collected for all subjects, who have provided consent, at a subset of the study sites participating in this study.

Subjects will have full face and side view photographs taken and anonymized prior to Sponsor use.

Study sites selected for photography will be trained and receive standardized photographic equipment by a centralized photographic vendor. Photographs will be electronically transferred from the site to the vendor.

At the end of the study, the site will receive an electronic file of all subject photographs for archiving.

The central photography vendor will tabulate and transfer all subject photos to the Sponsor during the course of the study.

9.3.2 Acne Patient Self-Questionnaire

Subjects will be asked to complete Acne Patient Self-Questionnaire. The questionnaire is paper-based and will be completed by subjects during clinic visits (see Appendix 2). Subject responses will be entered in the eCRF by the study site and the completed questionnaires kept as part of the subject's source document. Study site staff must review all forms to ensure complete responses prior to a subject leaving the study site.

9.4 Assessment of Safety

9.4.1 Physical Examination

A complete physical examination will be conducted at screening and Week 12 or Early Termination visits and cover general appearance, dermatological, head, ears, eyes, nose, throat, respiratory, cardiovascular, abdominal, neurological, musculoskeletal, and lymphatic body systems. Height and weight will be recorded as part of the screening physical exam and only the subject's weight will be recorded with the end of study physical exam. A symptom-directed physical exam may be performed at subsequent visits as needed. Following baseline, any new findings or findings that have worsened in severity should also be recorded as an AE.

Physical exam findings will be recorded in the eCRF.

9.4.2 Vital Signs

Vital signs, including body temperature, respiratory rate (breath per minute), pulse (beats per minute), and blood pressure (mmHg), will be obtained with the subject in the seated position, after sitting for at least 5 minutes. Any abnormal findings which are new or worsened in severity and clinically significant, in the opinion of the Investigator, will be recorded as an AE.

Vital sign measurements will be recorded in the eCRF.

9.4.3 ECGs

12-lead ECG measurements will be obtained in all subjects. The subject should rest quietly for at least 5 minutes in a supine position prior to ECG collection. The ECG should be obtained either prior to the time of blood collection, or at least 15 minutes afterwards.

At screening, the Investigator will use the machine-read ECG to determine subject eligibility. The medical monitor may be consulted if needed for interpretation of ECGs.

All study sites will be supplied with standardized, validated digital 12-lead ECG (12-lead at 25 mm/sec reporting rhythm, ventricular rate, the RR interval, the PR interval, QRS duration, QT and QTcF intervals) equipment capable of recording, storing, and printing producing high resolution 12-lead ECG data by the central laboratory. Study sites will be trained on the use of the equipment prior to study start.

Machine-read ECG recordings will be collected and analyzed centrally. Data will be transferred electronically to the database.

9.4.4 Laboratory Evaluations

Laboratory tests will be collected to evaluate safety in all study subjects and analyzed using a central laboratory. Labs will be collected per the Schedule of Visits and Procedures (see Appendix 1) or more frequently as clinically indicated. Laboratory samples are to be shipped on the same day as collected. No more than 4 mL/kg total will be collected over an 8 week period in subjects under legal adult age. Laboratory tests are described below.

Hematology: hematocrit, hemoglobin, red blood cell (RBC) count, white blood cell count and differential (%), mean corpuscular hemoglobin (MCH), mean corpuscular hemoglobin concentration (MCHC), mean corpuscular volume, platelet count, absolute neutrophils, absolute lymphocytes, absolute monocytes, absolute eosinophils, and absolute basophils. RBC morphology should be performed if indicated.

Chemistry: sodium, potassium, chloride, calcium, phosphorus, bicarbonate, uric acid, blood urea nitrogen (BUN), creatinine, total protein, albumin, aspartate aminotransferase (AST), alanine aminotransferase (ALT), alkaline phosphatase, bilirubin (total and direct), and glucose (fasting or non fasting).

Serum pregnancy testing will be performed at the screening and Week 12 (study exit) or Early Termination visits. Urine pregnancy testing (beta human chorionic gonadotropin [β -hCG]) will be performed at Baseline/Day 1, and the Weeks 4 and 8 visits for all females unless postmenopausal/sterile.

Urinalysis: pH, specific gravity, protein, glucose, ketones, bilirubin, blood, nitrite, urobilinogen, leukocyte esterase. A microscopic examination of urine will be performed if clinically indicated (e.g. a positive dipstick for protein, blood, leucocyte esterase) in the opinion of the Investigator based on the findings of the urinalysis or clinical signs and symptoms. Any new or worsened clinically significant laboratory result is to be recorded as an AE after study drug dosing.

Screening laboratory values must be reviewed by the Investigator prior to subject enrollment. Subjects will be screen failed for clinically significant laboratory values. Screening laboratory tests may be repeated one time in order to confirm out of range results clinical significance at the discretion of the investigator.

The central laboratory must be used for any laboratory testing required for a subject during study participation, including laboratory testing needed for unscheduled visits. If an immediate result is required to adequately care for a subject, a duplicate sample may be submitted to a local lab. Clinically significant laboratory results must be recorded as an AE, preferably as a diagnosis rather than individual test results. Any subject who has a clinically significant laboratory test result will be evaluated by the Investigator, and will be treated and/or followed up until the value returns to clinically acceptable level, in the opinion of the investigator.

9.4.5 Local Skin Reactions (LSRs)

All subjects will be assessed for LSRs, on the face, at each visit. LSRs include burning/stinging, pruritus, erythema, dryness and peeling. Each LSR will be scored as 0 (None), 1 (Mild), 2 (Moderate) or 3 (Severe). LSRs observed on a visit day will not be recorded as adverse events

unless scored as 3 (Severe). Local skin reactions experienced by the subject in between study visits are to be recorded as an AE.

Burning/stinging and pruritus will be assessed by the subject (Table 3) and erythema, dryness and peeling will be assessed by the Investigator/designee (Table 4). Subjects will be read the definition of each subject-assessed LSR and asked to select the appropriate definition. The corresponding score will be assigned by the site and entered in the eCRF.

Table 3: Subject Assessed Local Skin Reactions

Score	Grade	Burning/Stinging	Pruritus
0	None	No stinging/burning	No pruritus
1	Mild	Slightly warm, tingling sensation; not really bothersome	Occasional, slight itching/scratching
2	Moderate	Definite warm; tingling/stinging sensation that is somewhat bothersome	Intermittent itching/scratching which does not disturb sleep
3	Severe	Hot, tingling/stinging sensation that has caused definite discomfort	Bothersome itching/scratching which disturbs sleep

Table 4: Investigator Assessed Local Skin Reactions

Score	Grade	Erythema	Dryness	Peeling
0	None	None	None	None
1	Mild	Slight erythema: very light- pink	Perceptible dryness with no flakes or fissure formation	Mild diffuse peeling
2	Moderate	Dull red, clearly distinguishable	Easily noted dryness and flakes but no fissure formation	Moderate diffuse peeling
3	Severe	Deep/dark red	Easily noted dryness with flakes and fissure formation	Moderate to prominent, dense peeling

9.4.6 Adverse Events

An adverse event (AE) is defined as any untoward medical occurrence associated with the use of a study drug in humans, whether or not considered drug related. An AE can, therefore, be any unfavorable and unintended sign (including an abnormal laboratory finding), symptom or disease temporally associated with the use of the study drug, whether or not related to the investigational product.

AEs will be monitored throughout the study. Subjects will be instructed to inform the Investigator and/or study staff of any AEs. At each visit, subjects will be asked about AEs in a non-specific manner using open-ended questions so as not to bias the response (e.g., How have you been since the last visit?). Specific inquiry regarding reported AEs will be conducted when applicable. All AEs will be documented and recorded in the subject's eCRF.

Any subject who has an AE (serious or non-serious) or clinically significant abnormal laboratory test value will be evaluated by the Investigator, and will be treated and/or followed up until the symptoms or values return to normal or to clinically acceptable levels, as judged by the

Investigator. A physician, either at clinical site, or at a nearby hospital emergency room, will administer treatment for any serious adverse events (SAEs), if necessary. When appropriate, medical tests and examinations will be performed to document resolution of event(s).

9.4.6.1 Reporting

Only AEs that occur during or following study treatment with the study drug will be reported in the AE section of the eCRF. Events recorded prior to study treatment with the drug will be reported in the Medical History section of the eCRF as appropriate. All AEs occurring during the course of the study will be individually recorded in the eCRF. A condition that is present prior to administration of study drug and that worsens after administration of study drug should be reported as an AE. Information regarding the onset, duration, severity, action taken, outcome, and relationship to study drug will be recorded.

New or worsening abnormal laboratory values and/or vital signs are to be recorded as AEs if they are considered to be of clinical significance by the Investigator or meet the criteria of an SAE as described in Section 9.4.7.

Unless a diagnosis is available, signs and symptoms must be reported as individual AEs in the eCRF; a diagnosis is preferred.

The severity of an AE will be designated as mild, moderate or severe. The term "severe" is used to describe the intensity of an adverse event; the event itself, however, may be of relatively minor clinical significance (e.g. 'severe' upper respiratory infection). Severity is not the same as "serious". Seriousness of AEs is based on the outcome/action of an AE. (See Section 9.4.7.)

The relationship of the AE to the study treatment should be determined by the Investigator and will be based on the following two definitions:

Not related: An AE is defined as "not related" if the AE is not judged to be associated with the study drug and is attributable to another cause

Related: An AE is defined as "related" where a causal relationship between the event and the study drug is a reasonable possibility (possibly or probably related). A reasonable causal relationship is meant to convey that there are facts (e.g., evidence such as dechallenge/ rechallenge) or other clinical arguments to suggest a causal relationship between the AE and study treatment.

9.4.7 Serious Adverse Events

A Serious Adverse Event (SAE) is defined as any untoward medical occurrence that, at any dose,

- Results in death
- Is immediately life-threatening (i.e., in the opinion of the Investigator, the AE places the subject at immediate risk of death; it does not include a reaction that, had it occurred in a more severe form, might have caused death)
- Requires inpatient hospitalization or results in prolongation of an existing hospitalization

- Results in persistent or significant disability or incapacity
- Is a congenital anomaly or birth defect
- Is an important medical event that may not be immediately life-threatening, result in death, or require hospitalization, but may be considered an SAE when, based upon appropriate medical judgment, it jeopardizes the subject or may require medical or surgical intervention to prevent one of the outcomes listed above

As soon as the Investigator becomes aware of an AE that meets the criteria for an SAE, the SAE should be documented to the extent that information is available. A report must be submitted by the study site to the Sponsor or designee within 24 hours.

Any SAE, regardless of causal relationship, must be reported to the Sponsor immediately (within 24 hours of the Investigator's knowledge of the event).

SAEs will be recorded from the time of informed consent/assent, through to end of the study. If, in the opinion of the Investigator, an SAE occurring outside the specified time window, (i.e., following subject completion or terminations of the study) is deemed to be drug-related, then the event should be reported with 24 hours as outlined above.

The Investigator should institute any clinically necessary supplementary investigation of SAE information. In the case of subject death, any post-mortem findings/reports will be requested.

9.4.7.1 Reporting of Serious Adverse Events

All SAEs, as defined by the criteria above, must be reported to the Sponsor or designee using the SAE form provided, within 24 hours of the Investigator becoming aware of the event.

Serious adverse events must be recorded on an SAE form. The minimum information required for SAE reporting includes the identity of the PI, site number, subject number, event description, SAE term(s), reason why the event is considered to be serious (i.e., the seriousness criteria), and PI's assessment of the relationship of the event to study drug. Additional SAE information including medications or other therapeutic measures used to treat the event, and the outcome/resolution of the event should also be recorded on the SAE form.

In all cases, the Investigator should continue to monitor the clinical situation and report all material facts relating to the progression or outcome of the SAE. The Investigator may be required to provide supplementary information as requested by the Sponsor or its designee.

When reporting SAEs, the following additional points should be considered:

- When the diagnosis of an SAE is known or suspected, the Investigator should report the diagnosis or syndrome as the primary SAE term, rather than as signs or symptoms; signs, symptoms and tests that support the diagnosis should be provided
- Death should not be reported as an SAE, but as an outcome of a specific SAE, unless the event preceding the death is unknown. If an autopsy was performed, the autopsy report should be provided;

While most hospitalizations necessitate reporting of an SAE, some hospitalizations do not require SAE reporting, as follows:

- Hospitalization for elective or previously scheduled surgery or procedure for a preexisting condition that has not worsened after administration of study drug (e.g., a previously scheduled ventral hernia repair). SAEs must, however, be reported for any surgical or procedural complication resulting in prolongation of the hospitalization;
- Events that result in hospital stays for observation only of fewer than 24 hours and that do not require a therapeutic intervention/treatment (e.g., an emergency room visit for hematuria that results in a diagnosis of cystitis and discharge to home on oral antibiotics).

The Sponsor will process and evaluate all SAEs as soon as the reports are received. For each SAE received, the Sponsor will make a determination as to whether the criteria for expedited reporting to relevant regulatory authorities have been met.

The Sponsor will assess the expectedness of each SAE to the study treatment. The current Investigator's Brochure will be used as the reference document to assessed expectedness of the event to study drug.

9.4.8 Dosing Changes due to AEs

Dose interruptions are allowed should a subject experience intolerable treatment-related adverse events (e.g., pruritis) on study. In cases where the Investigator feels a dose interruption is warranted, the subject should be instructed to interrupt study drug application to allow symptoms to resolve. Subjects should be instructed to return to the twice daily application regimen within 2 days of dose interruption.

Dosing interruptions are to be recorded in the subject diary as a missed dose.

Study drug must be discontinued if an adverse event is deemed persistent and if continuation of study drug would not be in the best interest of the subject.

Refer to Section 10.3 for further information regarding discontinuation of study drug or early withdrawal.

9.4.9 Pregnancy

Should a subject become pregnant during study participation, study drug dosing will be discontinued and the subject will be withdrawn from study. The Investigator must perform medical assessments as clinically indicated and continue to follow the subject for at least 4 weeks after delivery. Details for both the mother and baby must be obtained. Pregnancy is not itself an AE or SAE; however, maternal/fetal complications or abnormalities will be recorded as AEs or SAEs, as appropriate. The Investigator must complete a study-specific pregnancy form upon confirmation of a pregnancy. Pregnancy reporting forms will be provided to the study site.

10 STUDY DISCONTINUATIONS

10.1 Discontinuation of the Study

The Sponsor has the right to terminate or to stop the study at any time. Should this be necessary, both the Sponsor and the Investigator will ensure that proper study discontinuation procedures are completed. The entire study will be stopped if:

- Evidence has emerged that, in the collective opinion of the Investigators at each site with the concurrence of the Sponsor or the sole opinion of the Sponsor, makes the continuation of the study unnecessary or unethical
- The stated objectives of the study are achieved
- The Sponsor discontinues the development of the study drug

Regardless of the reason for withdrawal, all data available for the subject at the time of discontinuation of follow-up must be recorded in the eCRF. All reasons for discontinuation of treatment must be documented.

10.2 Early Study Termination of Study Subjects

The Investigator will make every reasonable effort to keep each subject in the study; however, a subject may voluntarily withdraw from study participation at any time. If the subject withdraws consent and discontinues from the study, the Investigator will attempt to schedule an Early Termination visit as soon as possible, determine the reason for discontinuation, and record the reason in the subject's study records and in the eCRF.

If at any time during the study, the Investigator determines that it is not in the best interest of the subject to continue, the subject will be discontinued from participation. The Investigator can discontinue a subject at any time if medically necessary. The Investigator may discontinue a subject's participation if the subject has failed to follow study procedures or to keep follow-up appointments. Appropriate documentation in the subject's study record and eCRF regarding the reason for discontinuation must be completed.

All subjects who fail to return to the study site for the required follow-up visits will be contacted by phone to determine the cause(s) why the subject failed to return for the necessary visit or elected to discontinue from the study. If a subject is unreachable by telephone after a minimum of two documented attempts (one attempt on two different days), a registered letter will be sent requesting that subject contact the site regarding study follow-up.

Subjects will be discontinued early from the study if any of the following occur:

- Withdrawal of informed consent (subject's decision to withdraw for any reason)
- Any clinical adverse event, laboratory abnormality, or inter-current illness which, in the opinion of the Investigator, indicates that continued treatment and/or participation in the study is not in the best interest of the subject
- Death

- Serious protocol violation, including persistent noncompliance or subject requiring medication or procedures prohibited by the protocol, to allow subjects to receive the appropriate medical attention.
- Discontinuation of the study by the Sponsor

10.3 Study Drug Discontinuation

For subjects who decide to prematurely discontinue study drug treatment, all reasonable efforts should be made to obtain all protocol-specified safety assessments and end of study procedures.

The Investigator should stop study drug treatment in the following instances:

- Inter-current illness that would, in the judgment of the Investigator, affect assessments of clinical status to a significant degree.
- Any clinical adverse event which is clinically significant and is deemed persistent and probably or definitely related to study drug in the judgment of the Investigator.
- Unacceptable toxicity

11 STATISTICAL CONSIDERATIONS

11.1 General Statistical Methodology

All statistical processing will be performed using SAS® unless otherwise stated. No interim analyses are planned. Except where noted, all statistical tests will be two-sided and will be performed at the 0.05 level of significance.

Descriptive statistics will be used to provide an overview of the efficacy and safety results. For categorical parameters, the number and percentage of subjects in each category will be presented. For continuous parameters, descriptive statistics will include n (number of subjects), mean, standard deviation (SD), median, minimum and maximum. Appropriate inferential statistics will be used for the primary, secondary, and exploratory efficacy variables.

The primary method of handling missing efficacy data will be the method of Markov Chain Monte Carlo (MCMC) multiple imputation.

Demographic data will be summarized by treatment group using descriptive statistics. Subjects' baseline characteristics related to efficacy analyses will be compared between treatment groups to evaluate baseline balance between the treatment arms.

The number of subjects in each analysis set will be summarized. Reasons for study withdrawal during the blinded study will be summarized using frequencies and percentages by treatment group.

The primary method of dichotomizing the IGA score will be to consider a subject a "success" if the IGA at a post-baseline visit is 0 or 1 and 2 or more grades lower than at baseline; otherwise the subject will be considered a treatment "failure".

A statistical analysis plan (SAP), describing all statistical analyses will be provided as a separate document. The SAP will be finalized prior to unblinding of the study treatments.

11.2 Populations Analyzed

Listings and summaries will be provided for all randomized subjects.

Approximately 700 subjects with acne vulgaris on the face will be randomized, in a 2: 1 fashion, to Olumacostat Glasaretil Gel, 5.0% BID, or Olumacostat Glasaretil Gel, Vehicle. Efficacy analyses will be performed using the intent-to-treat (ITT) population and the per-protocol (PP) population. Safety analyses will be performed using the safety population.

All subjects who are randomized and dispensed study drug will be included in the ITT population.

All subjects who are randomized, receive at least one confirmed dose of study drug and have at least one post-baseline safety assessment will be included in the safety population.

The PP population will include all subjects in the safety population who complete the Week 12 evaluation without any significant protocol violations (i.e., any subject or investigator activity that could have possibly interfered with the therapeutic administration of the treatment or the precise evaluation of treatment efficacy). The PP population will include subjects in the safety population who do not meet any of the following criteria:

- Violated the inclusion/exclusion criteria;
- Have taken any interfering concomitant medications;
- Did not attend the Week 12 visit;
- Have missed both the Week 4 and Week 8 study visits;
- Have not been compliant with the dosing regimen (i.e. subjects must apply 80–120% of the expected applications of study medication during participation in the study);
- Out of visit window at the Week 12 visit by ± 5 days;

Subjects that discontinue from the study due to an adverse event related to study treatment or documented lack of treatment effect will be included in the PP population. Prior to breaking the blind, other additional criteria may be added to the list to accommodate for unforeseen events that occurred during the conduct of the trial that result in noteworthy study protocol violations.

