6.5 Study Drug Application

Subjects will be instructed on the application of the study medication. The first dose of the study drug will be applied in the clinic for instructional purposes. Subjects are to apply the study drug twice daily (morning and evening) to a clean dry face.

Study drug is to be applied topically, to the entire face (forehead, nose, cheeks, and chin) by squeezing approximately ½ inch or slightly more than 1 centimeter long line of gel, onto a finger and spreading the gel over the face, avoiding the skin around the eyes, eyelids and mouth, until the face is completely covered.

Subjects are to be instructed to wash their hands prior to and immediately following study drug application.

Subjects should avoid washing the face or swimming within 2 hours after applying study medication.

Missed doses should be applied, provided there is at least an 8 hour window until the next scheduled dose.

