8.1 Screening (Day -35 to -1)

The screening evaluation period may take up to 35 days in order to provide adequate washout time for subjects taking certain medications. The purpose of the screening visit is to ensure that appropriate subjects are entered into the study and remain stable during the pre-treatment period. Questions on eligibility will be referred to the Sponsor or their designee. Screen failures may be re-screened one time and must be assigned a new screening number. Screen failure information will be recorded in the eCRF. Screening procedures, excluding lab evaluations, may be done any time during the screening period (prior to dosing on Day 1) and after the subject has given informed consent.

- Obtain written informed consent/assent. For subjects under legal adult age, both parents or legal representatives may be required to sign informed consent as applicable.
- Collect demographic information
- Complete medical history
- Query subject for concomitant medication use
- Perform a complete physical examination
- Record height and weight
- Measure vital signs
- Assess Inclusion/Exclusion criteria
- Collect a 12 lead ECG
- Draw blood samples for laboratory tests and urine for urinalysis. Include serum pregnancy test for women of childbearing potential
- Determine concomitant medication washout duration
- Schedule next visit

8.2 Baseline Visit/ Day 1

Evaluations are to be done prior to the first dose of study drug

- Collect concomitant medication information
- Conduct a symptom-directed physical exam update medical history if appropriate
- Measure vital signs
- Conduct urine pregnancy test for women of childbearing potential
- Conduct Investigator Global Assessment (IGA)
- Collect acne lesion counts
- Collect Acne Patient Self- Questionnaire
- Evaluate face for pre-treatment local skin reactions (LSRs)
- Collect photographs (selected sites)
- Confirm subject eligibility (Inclusion/Exclusion criteria) and randomization to treatment
- Instruct subject on study medication application and diary completion
- Weigh tubes and dispense study drug and diary. Observe subject administering first dose
- Schedule all subsequent visits

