Informed Consent/Assent	X	, _	(, =	(, =,)	(, , , , , , , , , , , , , , , , , , ,	(' ' ' ' ' ' ' ' ' ' ' ' ' ' ' ' ' ' '	(, , , , , , , , , , , , , , , , , , ,
Demography	X						
Medical History	X						
Inclusion/Exclusion Criteria	X	X					
Complete Physical Exam, Height ^c , Weight	X						X
Symptom-directed Physical Exam		X	X		X	X	
Vital Signs	X	X	X		X	X	X
Adverse Events		X ^a	X	X	X	X	X
Local skin reactions		X	X		X	X	X
Concomitant Medications	X	X	X	X	X	X	X
12-Lead ECGs	X						X
Safety labs: Serum Chemistry, Hematology, Serum Pregnancy, Urinalysis	X						X
Urine Pregnancy Test		X			X	X	
Investigator Global Assessment		X			X	X	X
Acne Patient Self-Questionnaire		X			X	X	X
Acne Lesion Counts		X			X	X	X
Photographs ^b		X			X	X	X
Dispense Study Medication/Diary		X	X		X	X	
Study Medication Compliance			X		X	X	X

AEs to be collected after the first dose of study drug is applied. Selected sites only.
Height not required at Week 12.

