7.8.3 Safety Population

All subjects in the randomized population who receive at least one confirmed dose of study drug and have at least one post-baseline safety assessment will be included in the safety population and will be analyzed according to the treatment they received. All safety analyses will be performed using the safety population.

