7.9.1 Baseline Definition

Baseline is defined as the last non-missing assessment prior to the first dose of study drug.

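### The safety population leaves out subjects known to have been dosed if they have no post-baseline safety assessment, a term that neither document defines

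*Protocol*

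**What the plan says.** Protocol 11.2 admits to the safety population randomized subjects who "receive at least one confirmed dose of study drug and have at least one post-baseline safety assessment will be included in the safety population". SAP 7.8.3 keeps both conditions, analyzes by treatment received, and adds: "All safety analyses will be performed using the safety population". No set defined by dosing alone is given, and the randomized population in SAP 7.8.1 is not assigned any safety table.

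Other provisions bear on who meets the second condition:

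- **First dose.** Protocol 6.5: "The first dose of the study drug will be applied in the clinic for instructional purposes". The Day 1 list in Protocol 8.2 adds "Observe subject administering first dose", and places the Day 1 evaluations before that dose.
- **AE collection.** A footnote to the schedule in Protocol Appendix 1 reads "AEs to be collected after the first dose of study drug is applied". SAP 7.9.1: "Baseline is defined as the last non-missing assessment prior to the first dose of study drug".
- **Local skin reactions (LSRs).** Protocol 9.4.5 does not count a reaction seen on a visit day as an AE unless it is severe, but "Local skin reactions experienced by the subject in between study visits are to be recorded as an AE".
- **Early leavers.** For a subject who withdraws, Protocol 10.2 says "the Investigator will attempt to schedule an Early Termination visit as soon as possible". Protocol 8.8 allows unscheduled visits for subjects with AEs.
- **Very early visits.** SAP 7.9.2 does not analyze early termination or unscheduled visit data from before study day 5, apart from baseline values.

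**The concern.** A safety denominator should contain everyone exposed. Here the observed Day 1 dose establishes exposure, and the plan then adds a condition on what happened afterwards. A subject who is dosed, goes home and provides no further safety information is removed from the AE, LSR and exposure summaries, although treatment is documented. Early intolerance is one reason why such a subject might not return, so the removal may be related to the outcome being summarized.

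The undefined term adds to the problem. On a narrow reading, the subject needs a performed assessment such as an LSR score, vital signs or laboratory tests. An AE known only from a phone call would then stay out of the AE tables, even though SAP 7.9.8.2 treats any AE with onset on or after first application as treatment-emergent. On a broad reading, an AE report is itself an assessment. A dosed early leaver who reports an event then enters the set, while one who is never heard from does not. Nothing in the plan chooses between the two. Safety is half of the study objective, so the choice should not be left until the data are in hand.

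**Working it through.** The plan states no figure for early loss or for the size of the safety population, so there is none to reproduce. The check has two parts.

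**1. Who is excluded**

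| Situation after the Day 1 dose | In the safety population? |
|---|---|
| Attends Week 1 | Yes |
| Early termination or unscheduled visit before Week 1 | Yes on the wording. If the visit is before day 5, its LSR and vital-sign data are not analyzed (SAP 7.9.2), and the plan does not say whether such a visit still qualifies |
| AE reported by phone only | Yes on the broad reading, no on the narrow one |
| Mild or moderate reaction seen in clinic after the first dose, no later contact | Unclear: Day 1 LSRs are scored before the dose, and a visit-day reaction below severe is not an AE (Protocol 9.4.5) |
| No safety information at all after the dose | No |

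The last row is excluded on any reading. The two rows above it depend on the undefined term.

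**2. How many, and with what effect**

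Inputs: planned arms of 467 and 233 (Protocol 6.3; 700 × 2/3 = 466.7 and 700/3 = 233.3). The excluded fraction f is my assumption, 0.5% to 3%.

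Number excluded = f × arm size. At 0.5%: 467 × 0.005 = 2.3 and 233 × 0.005 = 1.2, so about 2 and 1. At 3%: 467 × 0.03 = 14.0 and 233 × 0.03 = 7.0, so about 14 and 7.

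*Common event, broad reading.* Suppose that early leavers with an AE are kept and those without are dropped, and that the true incidence is p in both groups. The reported rate is p / (1 − f(1 − p)). With p = 10%, assumed:

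- f = 1%: 0.10 / (1 − 0.009) = 10.1%
- f = 3%: 0.10 / (1 − 0.027) = 10.3%

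*Rare early event, narrow reading.* Suppose that 5 active subjects in the set have the event (an assumed count). The table compares the reported rate with the rate among all 467 dosed, from none to all of the excluded having had it.

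| f | Excluded, active / vehicle | Reported rate, active | All dosed, none of the excluded affected | All dosed, all of the excluded affected |
|---|---|---|---|---|
| 0.5% | 2 / 1 | 5/465 = 1.08% | 5/467 = 1.07% | 7/467 = 1.50% |
| 1% | 5 / 2 | 5/462 = 1.08% | 5/467 = 1.07% | 10/467 = 2.14% |
| 2% | 9 / 5 | 5/458 = 1.09% | 5/467 = 1.07% | 14/467 = 3.00% |
| 3% | 14 / 7 | 5/453 = 1.10% | 5/467 = 1.07% | 19/467 = 4.07% |

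The last column is an upper bound, not an expectation. The intent-to-treat (ITT) set needs only randomization and dispensing (SAP 7.8.2), so the ITT efficacy analyses and their power are unaffected.

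**The case against.** A reader might infer that everyone who leaves before Week 1 drops out of the safety tables, including anyone who left because of a first-dose reaction. The documents do not support that. The test is having no post-baseline safety assessment, not missing Week 1. An early termination visit is sought promptly and covers AEs, LSRs, vital signs, laboratory tests and ECG (Protocol 8.7), and subjects who fail to return are phoned (Protocol 10.2). AE collection starts with the Day 1 dose, and baseline precedes that dose, so a reaction recorded afterwards can count as post-baseline. The narrow reading is also the weaker one: SAP 6.2 names AEs first among the means of assessing safety, and Protocol 9.4 places AEs under safety assessment. Most reported first-dose reactions would therefore bring the subject in.

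Other points on this side also stand. The rate of early loss is assumed. The vehicle has the same ingredients apart from the active substance, so irritation from the alcohol base does not by itself imply a different loss by arm. Excluded subjects appear in the summary of reasons for exclusion (SAP 7.9.3), SAP 7.9.8.2 plans listings of all AEs, and there is no between-group inference on AEs.

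These points narrow the concern but do not remove it. Early termination visits are attempted, not assured, and unscheduled visits are optional. The Day 1 list in Protocol 8.2 has no AE line, and a mild or moderate reaction in clinic need not become an AE. A listing does not supply an incidence or a denominator. The day-5 rule also means that an early visit can admit a subject while its LSR data go unsummarized.

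**Conclusion.** The concern holds in limited form. The rule removes subjects with documented exposure from all safety summaries and denominators when they have no later safety assessment, and it does so through an undefined term. Some of those removed may have left because of early intolerance; the documents do not show that any did, or how many.

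At an assumed 0.5–3%, about 2–14 of 467 active and 1–7 of 233 vehicle subjects are affected. For a common event the distortion is small: at 1–3% excluded, an assumed 10% is reported as 10.1–10.3% on the broad reading. For a rare early event it could matter, but only if the excluded subjects are largely those who reacted and their reactions were not counted. The figures do not support a claim that overall AE incidence is materially understated. The change is worth making because the condition is unnecessary when the first dose is observed and costs almost nothing to remove.

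**What to change.** 1. In Protocol 11.2 and SAP 7.8.3, define the safety population as all randomized subjects with at least one confirmed dose of study drug, analyzed by treatment received.
2. Use it for the AE and exposure tables. Let by-visit LSR, vital sign, laboratory and ECG tables use subjects with data at that visit.
3. Write the post-baseline condition into the PP definition (Protocol 11.2, SAP 7.8.4). PP is drawn from the safety population and admits subjects who discontinue for a related AE or documented lack of effect, so without this step it would widen.
4. In SAP 7.9.2, state how LSR and other safety data from early termination or unscheduled visits before day 5 are reported, for example by including them in the worst post-baseline LSR summary of SAP 7.9.8.4. Step 1 alone does not recover these data.

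The cost is a few sentences in two documents, with an entry in SAP section 5, before unblinding. No new data are collected. The downside is that a few subjects with little or no follow-up enter the AE denominators, which can slightly dilute observed rates. They can be identified in a footnote.
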